2. Determine differences in range of motion of the affected joint in the corticosteroid plus lidocaine group as compared to the corticosteroid alone group.
3. Determine differences in patient-reported outcome scores (VAS-pain, qDASH, PRWE, ASES, SF12, EQOL) in the corticosteroid plus lidocaine group as compared to the corticosteroid alone group.
4. Report patient characteristics associated with efficacy of addition of lidocaine to corticosteroid injectate for pain and ROM resolution (type of injury, affected joint, age, BMI, comorbidities, etc.).

Hypotheses:

Hypothesis⁰: Corticosteroid injectate alone will result in statistically significant reduced pain scores as compared to corticosteroid with lidocaine for the treatment of tenosynovitis.

Hypothesis¹: Lidocaine plus corticosteroid injectate will result in equivalent requirements for repeat injection or conversion to surgery as compared with corticosteroid injectate alone for the treatment of tenosynovitis.

Hypothesis²: Lidocaine plus corticosteroid injectate will result in equivalent patient reported outcomes scores as compared to corticosteroid alone for the treatment of tenosynovitis.

Hypothesis³: Lidocaine plus corticosteroid injectate will result in equivocal patient-reported outcome scores, ROM, and pain reduction as compared to corticosteroid alone for the treatment of tenosynovitis.

Study Design

This will be a randomized control trial of a group of patients with upper extremity tenosynovitides treated with either lidocaine plus corticosteroid or corticosteroid injection alone by upper extremity fellowship trained surgeons at Emory University. Patients will be randomly assigned to one of two groups at the time of treatment: 1. Lidocaine Plus Corticosteroid and 2. Corticosteroid Alone. A random allocation sequence, concealed in consecutively numbered, opaque, sealed envelopes, determining active treatment or placebo, will be computer generated. Written-informed consent will be obtained from patients prior to injection.

Patients in the Corticosteroid group will be treated with a 40 mg/mL injection of corticosteroid following sterile preparation. The volume of injectate differs for each tenosynovitis being treated. For example, trigger finger patients in the corticosteroid alone group will receive a 1mL of injectate total (consisting of 1 mL of 40mg/mL triamcinolone).

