Patients in the Corticosteroid and Lidocaine group will be treated with a 40 mg/mL injection of corticosteroid combined with 1% lidocaine. The volume of injectate differs for each tenosynovitis being treated. For example, patients being treated for trigger finger will receive 0.5 mL of 1% lidocaine and 1 mL of 40mg/mL triamcinolone.

Needle size and insertion site of needle differs for each tenosynovitis being treated. For trigger finger specifically, needle injections will be performed with an appropriately sized needle inserted over the A1 pulley at a 45-degree angle. The injection will be done with the same technique for both groups by the attending physician. The medication will be injected extra-synovially in order to make the treatment more reproducible. This method of injection has been supported in previous studies.

Outcome Measures:

- Likert Scale: A 10-point likert scale will be asked before and after injection which has been previously validated in other studies looking at efficacy and pain surrounding injections of the upper extremity.
- Pain Assessment: A pain assessment will be assessed before performing the injection, at the time of injection, and at each subsequent follow up visit. Pain scores will be obtained via the Visual Analog Pain Scale (VAS-pain), which is ranked from 0 (no pain) to 10 (highest amount of pain). Pain will be assessed at rest and active movement of the affected joint. Patient will also be asked to fill out the VAS-pain score twice daily in a pain journal (once in the morning and once at night) each day until post-injection day 7.
- qDASH/PRWE/ASES/SF12/EQOL score: These scores will be administered at each clinic follow up. They will also be administered 6 week after the injectate has been performed.
- Need for subsequent reinjection and surgical operation will be recorded.

These scores, specifically the 10-point likert, will also be assessed before performing the injection, immediately after the injection, and again at the various follow up appointments. During clinic follow up we will monitor for complications.

Inclusion Criteria:

- All adult clinical patients of Emory upper extremity surgeons undergoing injection for treatment of the following who are willing to participate in the study will be included in the study: Tenosynovitis of the upper extremity, including but not limited to, the shoulder, biceps, elbow, wrist, thumb, carpometacarpal, midcarpal, elbow, and small joints of the hand (PIP, DIP, MP).

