The minimally clinically important difference (MCID) varies for each outcome measure. Therefore, for the purposes of a power analysis, we will use the VAS-pain at the time of injection as the primary outcome. A similar study was published in 2017 from Earp *et al.* comparing needle-free jet lidocaine for pre-corticosteroid injection anesthesia with simultaneous lidocaine and corticosteroid injection. Using the results of this study as a metric, for the purposes of our study, to determine a 1-point change in VAS (4.5 to 3.5) with the reported standard deviation of 2 (SEM

was 0.4, with 30 subjects in each group) in the Earp *et al.* study, the number needed to treat to detect a difference between the treatment and placebo group would be 63 [32]. Therefore, we aim for a sample size of 63 patients for each possible tenosynovitis described in the inclusion criteria.

In total, **we plan to enroll 1000 patients total into this study** when combining all possible tenosynovitides encountered at Emory. These outcomes will be feasible to obtain in a reasonable time frame given the high volume of patients treated for tenosynovitis of all types at Emory. Patients will be grouped together for analysis and also broken into subgroups for sub-analysis based on primary diagnosis for injection.

JMP Pro Software or SPSS will be used to analyze the data and perform the statistics.

Risks to participation

Risks to participation include breach of confidentiality from PHI used to conduct the study. Every effort will be used to scrub data when possible and to use subject numbers/unique identifiers when possible.

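### Allocation is described as one envelope sequence with no mention of stratifying by diagnosis, although results will be analysed by diagnosis with unadjusted tests only

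*Combined protocol and SAP*

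**What the plan says.** The allocation method is given in two sentences of the Study Design section: "Patients will be randomly assigned to one of two groups at the time of treatment", and "A random allocation sequence, concealed in consecutively numbered, opaque, sealed envelopes, determining active treatment or placebo, will be computer generated". No ratio is stated. Blocking, stratification and minimisation are not mentioned there or anywhere else.

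The Statistical Analysis section makes diagnosis an analysis factor: "Patients will be grouped together for analysis and also broken into subgroups for sub-analysis based on primary diagnosis for injection". It also sets a size by diagnosis ("we aim for a sample size of 63 patients for each possible tenosynovitis described in the inclusion criteria") and a total ("we plan to enroll 1000 patients total into this study"). The list of sites under Inclusion Criteria is open-ended, and no minimum number per diagnosis is set.

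The tests named in the same section are the t test, Kruskal-Wallis, chi-square, Mann-Whitney and Wilcoxon signed-rank tests. None takes account of diagnosis.

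**The concern.** The diagnosis is the reason for the injection, so it is known before an envelope is opened. It is the planned subgroup factor, and the fourth objective names type of injury and affected joint as characteristics of interest. The Study Design section says that injectate volume, needle size and insertion site differ by condition. The outcome used for the power calculation is VAS-pain at the time of injection, which could plausibly vary with those features.

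If allocation takes no account of diagnosis, two things are left to chance: the arm sizes within each diagnosis, and the mix of diagnoses between the pooled arms. The planned tests neither correct for a difference in mix nor use diagnosis to reduce residual variance. At stake are some precision, and how easily the per-diagnosis comparisons can be presented.

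**Working it through.** **Inputs.** From the Statistical Analysis section: difference 1 VAS point, SD 2, two-sided 5% level, 63 patients for each diagnosis, 1000 in total. Assumed because not stated: 1:1 simple allocation and 80% power.

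**1. The plan's own figure.** n per arm = 2 × (1.960 + 0.842)² × 2² / 1² = 62.8, so 63. Power of 85% would give 72 and 90% would give 85, so 80% is the value that reproduces the plan. The formula gives 63 per arm, or 126 per diagnosis, whereas the text applies 63 to patients per diagnosis. Both sizes are carried forward.

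**2. Chance of an uneven split within a diagnosis**, exact Binomial(N, 0.5), both directions:

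| Patients in the diagnosis | 60:40 or worse | 2:1 or worse |
|---|---|---|
| 20 (illustrative) | 50% | 12% |
| 30 (illustrative) | 36% | 9.9% |
| 63 | 13% | 1.1% |
| 126 | 2.6% | 0.02% |

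The chance that at least one of K diagnoses splits 60:40 or worse is 1 − (1 − p)^K. With 63 patients in each of 8 to 12 diagnoses it is 67% to 81%. With 126 each, 1000 patients fill 1000/126 = 7.9 diagnoses, and for K = 8 the chance is 19%.

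**3. Cost of an uneven split.** Relative efficiency is 4p(1 − p) = 4 × 0.6 × 0.4 = 0.96 at 60:40. Power for a 1-point difference is Φ(1/SE − 1.960), with SE = 2 × √(1/n₁ + 1/n₂):

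- N = 63: equal arms, SE 0.504, power 51.0%. At 60:40, SE 0.514, power 49.4%.
- N = 126: equal arms, SE 0.356, power 80.1%. At 60:40, SE 0.364, power 78.5%.
- N = 20: equal arms, power 20.0%. At 12:8, power 19.4%.

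Averaged over all possible splits, the loss is below 1 point (51.0% to 50.3% at 63; 80.1% to 79.8% at 126).

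**4. Pooled case mix.** Suppose true diagnosis means vary with SD τ. With 500 per arm, the chance difference between arms due to case mix has SD τ × √(1/500 + 1/500) = 0.063τ. For an assumed τ of 0.5 to 1 point this is 0.03 to 0.06 points, against a target of 1 point.

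**5. Gain from adjusting the pooled analysis.** The share of outcome variance due to diagnosis is τ²/(τ² + 2²). For τ = 0.5 it is 0.25/4.25 = 6%, and for τ = 1 it is 1/5 = 20%. The standard error shrinks by 1 − √(4/4.25) = 3% to 1 − √(4/5) = 11%. SD 2 is treated as a within-diagnosis value because the trial it comes from is, by its title, in trigger finger.

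**6. What stratified blocks would give.** With blocks no larger than 4, the arms in a stratum differ by at most 2 patients. The worst split is 32:31 at N = 63, against 39:24 at the edge of the 95% range for simple allocation. At N = 126 it is 64:62, against 74:52.

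**The case against.** The strongest reply is that almost nothing is lost. At the powered size of 126, a 60:40 split is rare, and when it occurs it costs 1.6 points of power. A diagnosis with 20 patients is uninformative because it is small, not because it splits 12:8. Baseline differences within a small diagnosis also come from its size, and stratifying on diagnosis would not remove them. All of this stands, and it keeps the point minor.

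It can also be said that the text is silent rather than explicit: the list may be blocked, or there may be several lists. That stands too. A reader might infer that the plan has decided against stratification, but the documents do not say so. They describe a single sequence and say nothing more. A blocked list shared by all diagnoses would not in any case secure balance within each one.

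Finally, the documents give no pain data by diagnosis. A reader might infer that diagnosis is an established strong predictor of outcome here. The differences in volume, needle and site make some effect plausible, but its size is an assumption.

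What the reply does not remove is that the method as written leaves a planned analysis factor out of both allocation and analysis, and that including it is cheap.

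**Conclusion.** The point holds as a minor, inexpensive improvement. Under simple 1:1 allocation, a 60:40 or worse split has a 13% chance in a diagnosis of 63 and 2.6% in one of 126. The higher figures at 20 and 30 patients rest on illustrative sizes. Small diagnoses are possible, because the site list is open and no minimum is set, but their number and size are unknown.

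Two stronger readings should be resisted. Unequal arms do not bias the comparison, so the per-diagnosis results would not be invalid. Nor is there a material loss of power from imbalance: chance differences in case mix are also small in a pooled sample of 1000. The more useful gain is the 6% to 20% of outcome variance that adjustment could remove from the pooled comparison, subject to the assumed spread of diagnosis means. Whether 63 is meant per arm or per diagnosis matters more for power (80% against 51%), but that is a separate question.

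**What to change.** State the allocation ratio and how the list is generated. Use permuted blocks of varying size, stratified by diagnosis. Give each diagnosis that will be analysed on its own a separate stratum and envelope set, and use one combined stratum only for diagnoses that will not be. A broad residual stratum would not protect a small diagnosis that is later analysed separately. Record the primary diagnosis before the envelope is opened; it is not in the list of variables to be collected.

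In the pooled analysis, replace the unadjusted comparison with one adjusted for diagnosis: a linear model with diagnosis as a factor, or a stratified rank test such as van Elteren's. If enrolment has started, this adjustment alone is still available.

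The cost is several envelope sets to manage instead of one, and a model-based or stratified test in place of the simple two-group tests. Varying the block size limits how far the next assignment can be predicted.

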In addition, similar pathologies exist where the role of lidocaine remains vague. One such pathology is de Quervain tenosynovitis. de Quervain tendinopathy affects the abductor pollicis longus (APL) and extensor pollicis brevis (EPB) tendons in the first extensor compartment at the styloid process of the radius. It is characterized by pain or tenderness at the radial side of the wrist. Although de Quervain tendinopathy is often attributed to overuse or repetitive movements of the wrist or thumb, the cause is generally unknown. It most commonly affects women between the ages of 30-50 years old [28].

A small randomized trial found that glucocorticoid injections resulted in significantly better symptom improvement compared with placebo one week after injection [29]. Among those who responded to glucocorticoid injections, the beneficial effects were maintained during the 12-month follow-up period. Another randomized trial also found that splinting plus glucocorticoid injection was better than splinting alone [30]. Most patients experience pain relief after a single glucocorticoid injection [30, 31]. In patients with recurrent symptoms after initial relief with the

first glucocorticoid injection, a second injection may provide benefit. However, limited evidence is available about the role of lidocaine during these injections. We further aim to elucidate the role of corticosteroid and lidocaine versus corticosteroid alone in the treatment of de Quervain tenosynovitis.

Furthermore, the role of lidocaine with corticosteroid in the treatment of a number of other tenosynovitides remains ambiguous. These include tenosynovitis of the shoulder, biceps, elbow, wrist, thumb, carpometacarpal, midcarpal, elbow, and small joints of the hand (PIP, DIP, MP). We aim to ascertain whether the corticosteroid and lidocaine injectate together is as effective as corticosteroid in the treatment of these tenosynovitides. For all these pathologies corticosteroid with or without lidocaine is standard of care for orthopaedic hand and shoulder surgeons and the use of either treatment regimen is based on personal preference by the surgeon.

Objectives:

1. Determine differences in pain scores / likert scale at the time of injection and during follow up in the corticosteroid plus lidocaine group as compared to the corticosteroid alone group.

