- Between the ages of 18 years and 95 years.

- For trigger finger: patients with a diagnosis of stenosing tenosynovitis based on a history of triggering and the presence of tenderness over the A1 pulley upon clinical examination. All patients, based on the Quinnell grading of trigger finger see in the figure below, will be included.

Grade	Clinical findings (during flexion and extension)
0	Normal movement
I	Uneven movement
II	Actively correctable
III	Passively correctable
IV	Fixed deformity

Exclusion Criteria:

- Patients who are minors, vulnerable subjects, or who are not willing to consent to participate in the study.
- Allergies to glucocorticoids, current daily use of glucocorticoids or strong opioids (morphine, fentanyl, hydromorphone, ketobemidone, methadone, nicomorphine, oxycodone, and meperidine), severe diabetic neuropathy of the hand influencing pain perception, rheumatoid arthritis, and neurological or psychiatric diseases, potentially influencing pain perception.
- Subjects who, in the opinion of the investigator, may be non-compliant with study schedules or procedures.

Statistical Analysis:

Data will be stored on an excel spreadsheet. We will collect the name, medical record number, age at time of surgery, ethnicity, gender, BMI, presence of diabetes, Quinnell grading of trigger finger, smoking status, pre-injection VAS-pain, post-injection VAS-pain, 10 point likert scale, complications, and need for repeat injection or surgical release. It is possible that other variables may be added depending on analysis. Each variable will be used as a nominal variable when possible (e.g. smoking status) or a continuous variable if needed (e.g. VAS-pain, patient related outcome scores). For some statistical calculations we may break up the continuous variables in to ranges (e.g. Ages 15-20, 25-30). We will perform statistical analysis using unpaired, 2-tailed Student t test to compare means for normally distributed data, Kruskal-Wallis test to compare medians of non-normally distributed data, and chi-square test to compare proportions. Statistical significance will be interpreted as $P < .05$. Confidence intervals will be calculated with a confidence level of 95%.

Specifically, the 2 groups will be compared using the Mann-Whitney U test to analyze the difference between the post-injection VAS scores. The Wilcoxon sign-rank test will be used to test the difference between the treatment and control group for pain and patient related outcomes.

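### Several surgeons give the injections and pain at injection is the primary outcome, but the surgeon is not listed for recording and enters no planned test: a loss of precision, not a bias

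*Combined protocol and SAP*

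**What the plan says.** Study Design has patients treated "by upper extremity fellowship trained surgeons at Emory University", and Inclusion Criteria admit "All adult clinical patients of Emory upper extremity surgeons undergoing injection for treatment". There is therefore more than one operator; the number and their caseloads are not given.

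On technique, Study Design states: "The injection will be done with the same technique for both groups by the attending physician". It also states: "Needle size and insertion site of needle differs for each tenosynovitis being treated". For trigger finger it fixes the insertion point, the angle and extra-synovial placement, but leaves needle size to judgement.

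The sample-size text in Statistical Analysis says "we will use the VAS-pain at the time of injection as the primary outcome". The data list in that section covers patient characteristics, Quinnell grade and pain scores, and closes with "complications, and need for repeat injection or surgical release. It is possible that other variables may be added depending on analysis". The surgeon is not on it. The named tests (t test, Kruskal-Wallis, chi-square, Mann-Whitney, Wilcoxon) have no surgeon term or strata, and the only planned grouping is by primary diagnosis.

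On allocation, Study Design says: "A random allocation sequence, concealed in consecutively numbered, opaque, sealed envelopes, determining active treatment or placebo, will be computer generated". It mentions neither strata nor blocks.

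**The concern.** Pain felt at an injection plausibly depends in part on who gives it. Using the same technique in both arms stops that from favouring one arm, but it does not remove differences between surgeons. If such differences exist and the analysis ignores them, they stay in the residual variance of the primary comparison.

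At stake is precision in the diagnosis subgroups. Each is sized at 63 with no visible margin, so a source of variance that is known for every patient is worth removing if it is not trivial. Recording has to begin with the first patient: the Data safety and monitoring plan strips identifiers before analysis, and needle gauge may not be recoverable later.

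**Working it through.** **Inputs.** From Statistical Analysis: difference 1 point, SD 2, two-sided 5% level, 63 patients per diagnosis, 1000 in total. Not in the documents, so assumed: 80% power, 1:1 allocation, 63 read as per arm, and ρ, the share of VAS variance that lies between surgeons, at 2% to 20%.

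**1. The plan's own figure.** n per arm = 2 × (1.960 + 0.842)² × 2² / 1² = 2 × 7.85 × 4 = 62.8, so 63. The stated 63 reproduces as a per-arm number at 80% power. Under the same formula 90% power would need 85 and a one-sided test 50. If 63 is the total for a diagnosis, power is about 51%.

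**2. Baseline.** The 80.1% that the normal formula gives at 63 per arm becomes 79.5% for the t test with standardised effect 1/2 = 0.5.

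**3. Best case with the surgeon accounted for.** Residual SD = 2 × √(1 − ρ); standardised effect = 0.5 / √(1 − ρ); equivalent n per arm = 63 × (1 − ρ).

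| ρ (assumed) | Residual SD | Effect | t-test power at 63 per arm | Equivalent n per arm |
|---|---|---|---|---|
| 0 | 2.000 | 0.500 | 79.5% | 63 |
| 0.02 | 1.980 | 0.505 | 80.3% | 61.7 |
| 0.05 | 1.949 | 0.513 | 81.5% | 59.9 |
| 0.10 | 1.897 | 0.527 | 83.5% | 56.7 |
| 0.20 | 1.789 | 0.559 | 87.6% | 50.4 |

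This takes the SD of 2 to include surgeon variance already. If it is a within-surgeon SD, the unadjusted plan needs 65, 67, 70 or 79 per arm at these four shares, and its power at 63 (normal formula) is 79.3%, 78.1%, 75.9% or 70.9%.

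**4. Why it is a best case.** The formula charges nothing for estimating surgeon effects or for chance imbalance of surgeons between arms. Simulations of 126 patients with an assumed 4 or 8 surgeons and unstratified allocation show the cost:

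- With a random surgeon effect (variance share treated as known), the gain is almost nil at 2%, about 1 point at 5%, 2 to 3 points at 10% and 5 to 6 points at 20%.
- With fixed effects and 8 surgeons, power goes from 79.5% to 77.9% at 2% (a loss), from 79.9% to 79.5% at 5%, and from 79.9% to 81.4% at 10%. With 4 surgeons at 5% it goes from 79.9% to 80.9%.

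**5. Type I error.** In simulation it ran from 4.2% to 5.9%, near the nominal 5%, with or without a surgeon term.

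**6. Pooled analysis.** With 500 per arm, SE = 2 × √(2/500) = 0.1265. Multiplying by √(1 − ρ) gives 0.1233 at 5% and 0.1131 at 20%. Power for 1 point exceeds 99.9% throughout.

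**The case against.** The strongest reply is that nothing is wrong with the planned tests. Patients are individually randomised and each surgeon uses the same technique in both arms, so an unadjusted comparison is valid and the surgeon term is an optional efficiency gain. That stands. A reader might infer that ignoring the surgeon biases the result or inflates false positives; the design described does not support this, and the simulated error rates agree.

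It is also fair that the size of the gain is assumed throughout, that it vanishes at small shares, and that the pooled analysis does not need it for a 1-point difference. The sub-analysis by diagnosis may already absorb some surgeon and needle variation. All of this limits the weight of the point.

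The data list is open-ended and medical record numbers are collected, so the surgeon could probably be traced before de-identification. This helps only in part: the plan does not commit to recording the surgeon or to using it, and a covariate chosen after the data are in is weaker than one named beforehand.

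Three further readings go too far:

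- Background and Significance says that "the use of either treatment regimen is based on personal preference by the surgeon". That describes routine practice. In the trial the regimen is randomised, so the sentence is not evidence of between-surgeon variance in injection pain.
- A reader might take the allocation text to mean one sequence shared by all surgeons. The text is silent on strata.
- A reader might extend the point to reinjection and surgery, where the surgeon's threshold plausibly matters. No figure in the documents allows a size to be put on that.

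**Conclusion.** The point holds as a modest matter of precision. Several surgeons inject, pain at injection is the primary outcome, and the surgeon is neither listed for recording nor used in the analysis. The consequence is avoidable residual variance in the per-diagnosis comparisons. The best-case gain in power is 0.8 points at a 2% share (80.3 − 79.5), 2.0 at 5%, 4.0 at 10% and 8.1 at 20%. It is smaller with many surgeons or where each diagnosis is treated largely by its own surgeons.

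These figures rest on an assumed between-surgeon share, 63 read as per arm, equal arms, SD 2 and a t test. The matter becomes material only at shares of about 10% to 20%. It is worth acting on because the remedy is cheap and has to start at enrolment, not because the planned comparison is invalid.

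**What to change.** Add a coded injecting-surgeon identifier, and the needle gauge used, to the data list in Statistical Analysis from the start of enrolment. Keep both in the analysis file after de-identification.

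Pre-specify a surgeon-adjusted comparison of VAS-pain at injection with a random surgeon effect, and state whether it is the main or a supporting analysis. A random effect is preferable to fixed surgeon terms, which can lose a little power when there are many surgeons and small differences between them.

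Stratifying the envelopes by surgeon is optional. If it is done, block sizes should vary at random and be concealed. The surgeon can see the allocation: for trigger finger the volumes are 1 mL against 1 + 0.5 = 1.5 mL. A surgeon who tracks a series with fixed blocks of 4 would know one third of assignments in advance with certainty, and with fixed blocks of 6 one quarter. Fixed blocks could thus exchange a small gain in precision for possible selection bias.

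The cost is one or two extra fields and a model term. If surgeons differ little, the return will be little or nothing.
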